8. STATISTICAL CONSIDERATION AND DATA ANALYSIS PLAN

8.1 Analysis of baseline characteristics

To determine the demographics and characteristics of the patients in the two arms the following data will be collated:

- Age (yrs)
- Gender

IRAS ref 272362 Page **18** of **30**

• Height (kg), weight (cm), BMI

Distribution of data will be summarised but no inferential statistics will be applied in line with guidance [26].

Data concerning the actual meniscal repair procedure will also be collected, including:

- Exact meniscal surgery carried out (repair, partial meniscectomy, complete meniscectomy)
- Length of operation (min) and blood loss (ml) during operation
- Details on lavage procedure, if deviation from standard procedure.
- Type of anaesthetic and analgesics prescribed post-surgery
- Hospital length of stay (days)
- Moment physiotherapy and early recovery initiated, if applicable
- Any analgesics and/or anti-inflammatories administered and/or prescribed.

Any differences in distribution will be established with Chi-squared test or Mann-Whitney U-test/t-test (depending on distribution of data) as indicated.

8.2 Primary outcome statistics

To determine the level of operation-site related pain – at rest - experienced at day 7 post-operation (plus day 2, day 14, week 12 and week 26) and to compare the average pain scores of patients in the control and Viscoseal arm respectively, through administration of 100 mm visual descriptor scale (VDS) for pain. To compare the groups, the Mann-Whitney U-test will be applied.

The study is powered to detect the established minimal clinically important difference (MCID) of 15 mm on a 100 mm VDS pain.

In addition, VDS scale will be used for pain upon walking.

To avoid relying on one outcome measure related to pain, at 7 and 14 days post-surgery pain perception will also be measured using the short form McGill pain questionnaire. Again, to compare groups the Mann-Whitney U-test will be applied.

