1. LAY SUMMARY

Arthroscopic, or keyhole, surgery of the meniscus in the knee joint has benefits over open surgery. Nonetheless, there is scope to further improve outcomes for patients by reducing pain and discomfort and promoting enhanced recovery of knee joint functionality. The medical device Viscoseal contains hyaluronan and is designed to replenish levels of this compound in the knee joint following arthroscopic repair of the meniscus. Naturally, synovial fluid in the knee joint contains hyaluronan, but a lot of it is washed away when surgeons flush the knee joint during surgery to remove loose pieces of meniscus, cartilage, or bone. Previous studies, both in laboratory studies and patient trials, have demonstrated that Viscoseal can promote re-establishment of biological structure in the knee joint to allow it to return to a normal physiological state and protect cartilage. This present prospective, randomised, controlled trial aims to build on this evidence by comparing standard care versus the injection of Viscoseal (26 vs 26 patients) at the end of arthroscopic meniscus surgery. The degree of pain, leg swelling and knee functionality experienced by patients after surgery will be measured using validated patient surveys focused on the meniscus. The main objective is to determine if Viscoseal can achieve a minimal clinically important difference in pain relief after meniscal repair surgery when compared to standard care.

IRAS ref 272362 Page **7** of **30**

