5.5 Outcome measures

5.5.1 **Primary outcome measures**

To determine the level of index leg related pain experienced at day 7 post-operation and to compare the average pain scores of patients in the control and Viscoseal arm respectively, through administration of 100 mm visual descriptor scale (VDS) for pain at rest.

The study is powered to detect the established minimal clinically important difference (MCID) of 15 mm on a 100 mm VDS pain.

5.5.2 **Secondary outcome measures**

All the outcome measures are summarised in Table 2.

Table 2. Overview of measurements

Weeks	-12 weeks to day of surgery	48 hours	7 days*	14 days*	12 weeks#	26 weeks~
VDS pain scale for knee (at rest)	Х	Х	Х	Х	Х	Х
VDS pain scale for knee (walking)	Χ				Х	Χ
McGill pain questionnaire (at rest)	Х	X	X	Х		
Limb girth measurement (index leg)	X			Х	Х	
Lysholm scale	Χ				Χ	X
WOMET tool	Χ				Χ	Χ
Use of analgesics / anti- inflammatories	Х	X	Χ	Х	X	X
Patient satisfaction questionnaire re surgery						Χ
MRI scan (sub-study; not all participants)						Х

^{*} Allowed to be up to 2 days early or late

IRAS ref 272362 Page **13** of **30**

[#] Allowed to be up to 2 weeks early or late

[~] Allowed to be up to 4 weeks early or late

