6. SUBJECTS

6.1 Anticipated number of research subjects

The sample size calculation does take into account a 10% patient attrition rate (withdrawal and loss to follow-up), since this involves a study with multiple time points for data collection up to 26 weeks. Patients will be recruited from the adult population routinely seen by the evaluating clinical staff members. The primary outcome measure is based on knee/leg (ie wound site) pain experienced 7-days post-surgery based on the VDS pain scale (with leg at rest). The hypothetical difference in pain perception, based on a previous publication involving meniscal repair and Viscoseal, is 15mm on a 100 mm scale which equates to a significant 'minimally clinically important difference' for pain (Kelly 2001; Lee et al 2003; Tashjian et al 2009).

The non-parametric two-sided Mann-Whitney u-test is applied because the data is ordinal; 80% power and 5% significance is also applied. A priori power calculations using GPower 3.1 software, result in the following sample size summarized in Table 3.

It involves a minimum total of **52 participants**, who undergo meniscal repair surgery. Randomised 1:1, therefore 26 patients per arm.

Table 3, Sample size calculation

	Mean pain score (mm) at 7 days post-op~	Standard Deviation (hypothetical)
Viscoseal	28	20
Standard care	43	20

IRAS ref 272362 Page **14** of **30**

	Power beta of 80%, Alpha p-value of 0.05, Effect size 0.75			
	Sample size required without any drop-out: 48 samples.			
	Sample size with 10% attrition rate included: 52			
	Total of 52 patients:			
	26 Patients to receive standard care			
	26 Patient to receive Viscoseal			
~Based on Thein et al. 2	010			

For the MRI imaging sub-study a total of 24 patients will be recruited, 12 controls and and 12 viscoseal patients. This is in line with guidelines on pilot studies [25].

The CONSORT guidelines require a statement on the number of patients assessed for eligibility (Schulz, Altman & Moher 2010). The number of patients screened but who did not meet the inclusion criteria or who declined to participate will be recorded, as will any patients who are lost to follow-up (Appendix 3).

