6.1.1 Randomisation

Following written consent, participants are allocated at random to the control or Viscoseal intervention group, using a randomised sequence from the freeware randomisation programme, see https://www.randomizer.org/.

To take into account that not all patients will consent to taking part in the MRI sub-study, two randomisation sequences will be produced. One for patients who consent to both trial and MRI sub-study and one for patient who only consent to the main trial. This means:

- 24 patients for main trial + MRI sub-study (12 control and 12 Viscoseal)
- 28 patients for main trial only (14 control and 14 Viscoseal).

In this manner both control and Viscoseal arms are equally represented in the MRI sub-study and the remaining patients for the main trial are also equally distributed amongst the two study arms.

If one of the two randomisation blocks is full, then only the remaining block will be recruited to. However, North Cumbria Integrated Care is the only NHS Trust to conduct the MRI-substudy.

Sequential envelopes with each next randomisation allocation (for each randomisation block) will be used to achieve concealment and these will be kept in the research department. The researcher or regular healthcare professional for the participant in question can e-mail ([contact]) or phone the R&D Dept ([name]) to determine which treatment the next participant has been allocated to.

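### The only primary comparison is an unadjusted Mann-Whitney test: valid, but it leaves out baseline pain and the randomisation list and fixes no difference in mm to read against the 15 mm MCID

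*Protocol*

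**What the plan says.** - **Primary test.** Section 8.2 describes the aim as comparing average VDS pain scores between arms at day 7 and then fixes the method: "To compare the groups, the Mann-Whitney U-test will be applied". It names no covariate, no list or site term, no effect estimate and no confidence interval.
- **Reason for the test.** Section 6.1: "The non-parametric two-sided Mann-Whitney u-test is applied because the data is ordinal; 80% power and 5% significance is also applied".
- **Planning values.** Table 3 works in means: 28 against 43 mm, a column headed "Standard Deviation (hypothetical" with 20 mm in each arm, and "Power beta of 80%, Alpha p-value of 0.05, Effect size 0.75". It gives "Sample size required without any drop-out: 48 samples", and 52 after attrition.
- **Baseline.** Table 2 schedules "VDS pain scale for knee (at rest" before surgery as well as at day 7.
- **Allocation.** Section 6.1.1: "two randomisation sequences will be produced", one for patients who join the MRI sub-study (12+12) and one for the rest (14+14).
- **MCID.** Sections 5.5.1 and 8.2 say the study is powered for 15 mm. The lay summary goes further: "The main objective is to determine if Viscoseal can achieve a minimal clinically important difference in pain relief".
- **Other models.** Section 8.3 plans a Cox regression for pain, swelling and function. Its covariates are demographics, length of stay, type of anaesthetic and post-surgery analgesics. Baseline pain and randomisation list are not among them.

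**The concern.** A trial of 52 patients has little information to spare. Baseline pain on the same scale is recorded anyway and may explain part of the variation at day 7. The lists were built into the randomisation and are then dropped from the analysis. The Cox model does not fill the gap: a pain score is not a time-to-event outcome, the covariates omit the two that matter here, and some of them are measured after treatment.

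The second issue is interpretation. The sample size rests on a difference of means in mm, and the MCID is in mm, but the one fixed analysis yields a p-value for a rank comparison. If nothing else were reported, a reader could learn that the arms differ without learning by how much or how precisely. At stake are some power, protection against chance baseline imbalance, and a result that can be read against 15 mm.

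**Working it through.** **Inputs.** From Table 3 and section 6.1: difference 15 mm, SD 20 mm, d = 15/20 = 0.75, two-sided 5%, 24 per arm before drop-out, 26 per arm randomised. After 10% attrition, 26 × 0.9 = 23.4 per arm. Assumed: normal scores and a baseline/day-7 correlation r of 0.1 to 0.5.

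**1. The plan's own figure.** Power comes from the noncentral t with noncentrality d·√(n/2). For the Mann-Whitney test n is replaced by n·3/π, its relative efficiency for normal data. On the stated two-sided inputs, 80% power needs 31 per arm (62 in total), not 48. A one-sided Mann-Whitney calculation gives 24 per arm, which is 48. That mismatch is a separate sample-size matter; here it only sets the starting point.

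**2. Power of the planned test.** At 24 per arm the effective n is 24 × 3/π = 22.9 and the noncentrality is 0.75 × √(22.9/2) = 2.54.

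| Evaluable per arm | Mann-Whitney | Unadjusted t-test |
|---|---|---|
| 23.4 | 69% | 71% |
| 24 | 70% | 72% |
| 26 | 74% | 76% |

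Simulation (20,000 runs) gives 70.2% and 73.7% for the Mann-Whitney test at 24 and 26 per arm.

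**3. Power with baseline adjustment.** The residual SD is 20·√(1 − r²), so d becomes 0.75/√(1 − r²). One degree of freedom is charged for baseline; charging a second for the list changes power by less than 0.1 point.

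| r (assumed) | 1 − r² | adjusted d | ANCOVA power, 24 per arm |
|---|---|---|---|
| 0.1 | 0.99 | 0.754 | 72% |
| 0.2 | 0.96 | 0.765 | 74% |
| 0.3 | 0.91 | 0.786 | 76% |
| 0.4 | 0.84 | 0.818 | 79% |
| 0.5 | 0.75 | 0.866 | 84% |

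About 2 points of the gain over the planned test come from replacing ranks by means under normality (70% to 72%). Only the remainder comes from baseline.

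**4. Validity when the lists are ignored.** Simulated type I error of the unadjusted test with 12+12 and 14+14 patients is 4.8%, 4.6%, 4.3%, 3.4% and 2.7% for assumed shifts between lists of 0, 5, 10, 15 and 20 mm. The test becomes conservative, never liberal.

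**5. Significance against 15 mm.** The smallest observed difference with p<0.05 in a t-test is t × SD × √(2/n). At 26 per arm this is 2.009 × 20 × √(2/26) = 11.1 mm. At 24 per arm it is 2.013 × 20 × √(2/24) = 11.6 mm. An observed 15 mm at 24 per arm would have a 95% CI of 15 ± 11.6, that is 3.4 to 26.6 mm.

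**The case against.** The strongest reply is that nothing here is invalid. Sections 6.1 and 8.2 agree on the rank test and give a reason for it. Estimates, intervals and covariates are often left to a statistical analysis plan, which may exist. Since 8.2 speaks of average scores, arm means in mm are not excluded, and a Hodges-Lehmann shift with CI could accompany the test unchanged. Most of this stands, and it limits the point to efficiency and interpretability. It does not remove it: 8.2 does fix the primary comparison, and the ordinal argument sits badly with planning on means and an SD for a mark placed on a 100 mm scale.

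The gain from baseline is also uncertain. Baseline may be taken up to 12 weeks before surgery, while day 7 is post-operative pain, so a low r is plausible. At r = 0.1 to 0.2 the gain over an unadjusted t-test is only about 1 to 2 points.

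Four stronger readings are tempting but unsupported:

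- **That the MCID question cannot be answered.** This goes too far. Achieving the MCID is the stated aim only in the lay summary; section 4.1 asks about pain reduction. ANCOVA would not settle it at this size either: with 26 per arm, a lower 95% limit above 15 mm needs an observed 15 + 11.1 = 26.1 mm unadjusted, and about 25 to 26 mm adjusted at r = 0.3 to 0.5.
- **That ignoring the lists costs much power.** The lists exist because some patients will decline MRI. The documents give no ground for expecting a large pain difference between them.
- **That list stands in for site.** Only one Trust runs the MRI sub-study, but the protocol calls itself both multi-centre and single-centre, so no site effect can be sized.
- **That limb girth analysis is nearly powerless.** Section 8.3 lists the pre-surgery girth with the follow-up values and does not exclude change scores. The documents give no SD, effect or correlation for girth.

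**Conclusion.** The point holds as a worthwhile improvement, not a validity error. The fixed primary test leaves out baseline pain and the randomisation list, and its p-value alone does not supply the difference in mm that the planning and the MCID call for.

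On the protocol's d = 0.75, the planned test has about 69%, 70% and 74% power at 23.4, 24 and 26 per arm. ANCOVA at 24 per arm gives about 72% to 84% for r from 0.1 to 0.5. These figures rest on normal scores, on the hypothetical SD of 20 mm and on an assumed r. The interpretive part does not depend on r: about 11 mm observed at 26 per arm is already significant, so significance alone does not show 15 mm. Adjustment may recover some of the shortfall from 80% power, but that shortfall belongs to the sample-size calculation and should not be counted again here.

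**What to change.** Before any unblinded look at the data, including the interim analysis at 50% of the sample described in section 9:

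1. In 8.2, make the primary analysis an ANCOVA of day-7 VDS at rest on arm, baseline VDS at rest and randomisation list (MRI sub-study or main trial only).
2. Report the adjusted mean difference in mm with its 95% CI, read against 15 mm.
3. Keep the Mann-Whitney test as a sensitivity analysis, stratified by list (van Elteren) and accompanied by a Hodges-Lehmann shift in mm.
4. Adjust likewise for the baseline value when analysing limb girth, Lysholm and WOMET in 8.3.

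The cost is two degrees of freedom in the primary model and a wording change to the protocol, with any analysis plan brought into line. The baseline values and list membership are already collected.

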8.3 Secondary outcome statistics

The average baseline demographics for participants in each group will be compared to ascertain that randomisation has indeed led to comparable distribution of participants:

Sex, age, height, weight, BMI, length of stay, type of anaesthetic for surgery and type of analgesics post-surgery.

To compare outcomes between the two groups (standard vs Viscoseal), student t-test, Mann-Whitney U-test or Chi-squared test will be applied as applicable, depending on type and distribution of data .

IRAS ref 272362 Page **19** of **30**

Cox proportional hazards regression analysis will be conducted to investigate the role of Viscoseal and other covariates (as mentioned above) in post-surgery related pain, swelling and knee function.

The statistics apply to:

At least 2 weeks prior to surgery, and 7 days and 14 days post-surgery

- Indication of degree of swelling by measurement of thigh, suprapatellar and calf girth.

Up to 12 weeks prior to surgery, 12 weeks and 26 weeks post-surgery, knee function measurements: Lysholm and WOMET tools.

Descriptive safety overview post-surgery up to 26 weeks:

- Readmitted to theatre and/or hospital
- Infection of wound site
- Diagnosed with pulmonary embolism or deep vein thrombosis.

Patient satisfaction survey at 12 weeks and 26 weeks post-surgery – any difference in outcome will be determined with Mann-Whitney U-test

MRI diagnostics outcomes:

Descriptive statistics, primarily frequencies and averages, to summarise per intervention arm

- Type of injury
- Size of injury
- Grading of injury
- Any recurring or new meniscal injury

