3.2.2 Viscoseal (intervention) arm

Apart from the difference in terms of Viscoseal administration to the intervention group, the surgical protocol for the Viscoseal arm is identical to that of the standard care group. At the end of the surgery, again all the remaining fluids are drained from the knee, but this is followed by injection of 10 mL of Viscoseal preparation. Used Viscoseal product and syringes will be disposed of in line with local guidelines on disposal of clinical waste.

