5.3 Consent and recruitment

Those eligible will be approached and provided with an information pack and consent form, which will be signed to indicate that informed consent has been given. Patients will be given ample time to consider taking part, more than 24 hours if they wish. The study will be first mentioned at an orthopaedics out-patient clinic visit. The direct healthcare professional will first approach a patient about the study, and after verbal consent by the patient the healthcare professional themselves or a member of the research team can go through the informed consent process.

Patients are also allowed to consent to taking part when first approached as long as the study has been discussed with the patient and they have been given time to read the patient information leaflet and opportunity to ask any questions that they may have. Participants will receive no incentives and consent will be regarded as a process and not a one-off event. Participants are free to withdraw from the study at any time without the need to give any reasons for withdrawal. Their standard of care will not be affected by either declining to participate in the study or withdrawing during participation. Data collected up to the date of withdrawal will be retained for analysis.

Participants will be randomised to either the treatment as usual (TaU) or the intervention group (Viscoseal) any time up until the day of surgery. Study subjects who subsequently require additional significant surgical intervention, primarily ligament reconstruction, will be withdrawn from the study.

The MRI sub-study will be offered to all patients consecutively, and this will be done until the 24 required patients for said sub-study have been recruited.

5.4 **Follow-up**

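### Section 8.3 counts variables that arise after randomisation as baseline, uses them to check randomisation, and carries them into the secondary regression as covariates

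*Protocol*

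**What the plan says.** Section 8.3 opens with a check on randomisation: "The average baseline demographics for participants in each group will be compared to ascertain that randomisation has indeed led to comparable distribution of participants". The variables it names are "Sex, age, height, weight, BMI, length of stay, type of anaesthetic for surgery and type of analgesics post-surgery". Further down, the same section plans a Cox regression for the role of Viscoseal and of other covariates in post-operative pain, swelling and knee function. It identifies those covariates only by pointing back to what has been mentioned above.

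Section 8.1 treats two groups of variables differently. For age, gender, height, weight and BMI the rule is: "Distribution of data will be summarised but no inferential statistics will be applied in line with guidance". For data on the procedure, which include anaesthetic, analgesics and length of stay, it plans tests: "Any differences in distribution will be established with Chi-squared test or Mann-Whitney U-test/t-test (depending on distribution of data) as indicated".

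On timing, section 5.3 states: "Participants will be randomised to either the treatment as usual (TaU) or the intervention group (Viscoseal) any time up until the day of surgery". Section 3.2.1 confirms that allocation is known before the operation. Section 3.2.2 places the intervention at the end of surgery, once the knee has been drained: "this is followed by injection of 10 mL of Viscoseal preparation".

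Table 2 in section 5.5.2, introduced as the summary of the outcome measures, includes use of analgesics and anti-inflammatories at every time point. Section 8.2 compares the primary outcome, day 7 pain at rest, with a Mann-Whitney U-test and no covariates.

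**The concern.** A comparison can inform on randomisation only if the variable was settled before allocation. Three of the eight variables in section 8.3 were not, and two of those three come after the injection. The trial's hypothesis is that Viscoseal lowers post-operative pain. If it does, patients may need different analgesics, and the arms would then differ on a listed variable because the treatment worked. A reader of the randomisation check could not tell this from a flaw in allocation.

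The second consequence lies in the regression. If the list supplies the covariates, the model conditions on variables that the treatment may have changed. Its Viscoseal coefficient is then no longer the overall effect of the injection on pain, swelling or function.

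A separate and smaller matter is that section 8.1 rules out inferential statistics for the demographics, while section 8.3 takes the same variables and compares them with the aim of establishing that randomisation succeeded.

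**Working it through.** **Step 1: place each variable in time.** Randomisation is before surgery (sections 3.2.1 and 5.3); the injection is at the end of surgery (section 3.2.2).

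| Variable in 8.3 | Settled before randomisation? | Can follow from the injection? | Treatment in 8.1 |
|---|---|---|---|
| Sex, age, height, weight, BMI | Yes | No | Summary only, no inference |
| Type of anaesthetic | No, given at surgery | Unlikely | Tests planned |
| Length of stay | No | Yes | Tests planned |
| Type of post-surgery analgesics | No | Yes | Tests planned |

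Five of the eight variables are baseline. Three are not, and two of those three can carry a treatment effect.

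**Step 2: trace the list into the regression.** The covariates are defined only by a reference back. Within section 8.3 the one list of patient variables above that reference is this list. On the natural reading, length of stay, anaesthetic and post-surgery analgesics are candidate covariates.

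**Step 3: consider the bias.** If Viscoseal lowers pain and so leads to lighter analgesia, holding analgesics fixed removes part of the effect. But choice of analgesic also shares causes with pain that are not measured, and conditioning on a post-treatment variable can then bias the coefficient either way. The protocol does not say how strongly analgesics depend on treatment or on pain, so neither direction nor amount can be computed.

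**Step 4: could a real effect show up as an imbalance?** This is an illustration only. Inputs from section 6.1: 26 per arm and a 5% two-sided test. The effects are assumed.

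- Binary analgesic category, two-proportion normal approximation: power = Φ{[|p1 − p2| − 1.96·√(2p̄(1 − p̄)/26)] / √([p1(1 − p1) + p2(1 − p2)]/26)}, where p̄ is the mean of p1 and p2.
  - 30% v 50%: (0.200 − 0.266)/0.133 = −0.50, power about 31%.
  - 30% v 60%: (0.300 − 0.270)/0.132 = 0.22, power about 59%.
- Continuous variable, Mann-Whitney test by noncentral t with effective size 26 × 3/π = 24.8 per arm: power about 18% for a standardised effect of 0.3 and 41% for 0.5.

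A moderate true effect therefore has an appreciable chance of reaching significance if these variables are tested.

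**Step 5: the conflict with 8.1.** The no-inference rule covers the five demographics and no others. If each were tested at 5% and the tests were independent, the chance of at least one significant result under perfect randomisation would be 1 − 0.95^5 = 1 − 0.774 = 0.226, about 23%. BMI is computed from height and weight, so the tests are not independent and the figure is approximate.

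The protocol gives no figure of its own on this point to reproduce.

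**The case against.** **The check may be descriptive.** The sentence in section 8.3 says only that averages will be compared and names no test. The tests listed next are for comparing outcomes. A side-by-side table would agree with section 8.1. This stands, so the conflict with 8.1 is conditional. It does not rescue the list: even a descriptive comparison of post-injection variables says nothing about randomisation.

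**A reader might infer that section 8.1 forbids testing all eight variables.** It does not. It plans tests for procedure data, including the three at issue.

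**A reader might also apply the family-wise formula to all eight variables,** giving 1 − 0.95^8, about 34%. That figure needs eight independent tests that section 8.3 does not state. It also treats length of stay and analgesics as free of any treatment effect, when the difficulty is that they may not be.

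**A reader might infer that the plan would declare a Viscoseal benefit to be failed randomisation and then adjust it away.** Nothing in the protocol makes adjustment depend on an observed imbalance, or says how a difference would be interpreted.

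**The mechanism may be weak.** Same-day discharge is intended (section 3.2.1), so length of stay should vary little. The listed item is the type of analgesic, which section 8.1 records partly as what was prescribed, and this may respond less to pain than actual consumption. Both points reduce the likely size of the bias without removing it.

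**Analgesic use is already an outcome.** This is correct: Table 2 includes it. It strengthens the case for not using post-surgery analgesics as a baseline check or covariate.

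**Conclusion.** The point holds within limits. Section 8.3 misclassifies three post-randomisation variables as baseline. Two of them, length of stay and post-surgery analgesics, follow the injection, so they cannot test randomisation. As covariates they can bias the adjusted Viscoseal effect in the secondary regression, by an amount and in a direction that the documents do not allow to be calculated. This rests on reading the reference to covariates mentioned above as pointing to the list in the same section.

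The primary result is not at risk, because section 8.2 specifies an unadjusted Mann-Whitney comparison. The conflict with section 8.1 exists only if the comparison is inferential, and then only for sex, age, height, weight and BMI. Its size is about a 23% chance of at least one spurious imbalance, assuming five independent 5% tests.

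**What to change.** Amend section 8.3 as follows.

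- Limit the comparability table to the pre-randomisation variables (sex, age, height, weight, BMI), shown descriptively by arm as section 8.1 already provides.
- Delete the stated aim of establishing that randomisation succeeded.
- Report length of stay and post-surgery analgesics by arm as outcome or process data, and type of anaesthetic descriptively as procedure data.
- Replace the reference back to covariates mentioned above with a named list restricted to pre-randomisation variables.
- Align section 8.1 so that the variables moved out of the baseline list appear in one place with one treatment.

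The cost is a change of protocol wording. No new data, visits or patients are needed, and the primary analysis stays as it is.

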3.2 Intervention

3.2.1 Standard care (control) arm

All patients receive general anesthesia and a pneumatic tourniquet is used. Patients are already randomised prior to surgery to avoid delays with surgery and allow a vial of Viscoseal to be ready for the relevant patients. Joint irrigation is performed with the assistance of a manual arthroscopic pump using 0.9% NaCl solution at room temperature. Then, the remaining fluids are drained from the knee. At the end of the surgery, local anaesthetics is applied to the soft tissue of the arthroscopic portals [either 20 ml 0.5% Levobupivacaine (Chirocaine®), or 20 ml 0.75% Ropivocaine (Naropin®), or equivalent product], and the knee is dressed, while the tourniquet is still inflated. All surgeries are intended to be performed in a day-surgery facility with the patient being discharged the same day. Postoperatively, partial weight bearing with crutches is allowed. Crutches are recommended for the first 48 hours, primarily for patient safety by minimising the risk of a fall.

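### Section 8.3 names Cox regression for pain, swelling and function measured at fixed visits, and the covariates it most naturally refers to include two that arise after randomisation

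*Protocol*

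**What the plan says.** Section 8.3 of the protocol first assigns a t-test, Mann-Whitney U-test or Chi-squared test to the between-group comparisons, according to the data. It then adds that "Cox proportional hazards regression analysis will be conducted to investigate the role of Viscoseal and other covariates". The same sentence goes on to name the targets: "other covariates (as mentioned above) in post-surgery related pain, swelling and knee function".

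The list that stands above that sentence in Section 8.3 reads: "Sex, age, height, weight, BMI, length of stay, type of anaesthetic for surgery and type of analgesics post-surgery". It is introduced as a set of baseline demographics, to be compared as a check on the randomisation.

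The outcomes themselves are described as measurements. For pain, the aim given in Section 8.2 reads: "compare the average pain scores of patients in the control and Viscoseal arm respectively, through administration of 100 mm visual descriptor scale (VDS) for pain". For swelling, Section 8.3 gives: "Indication of degree of swelling by measurement of thigh, suprapatellar and calf girth". Knee function is the Lysholm and WOMET scores.

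On timing, Section 3.2.1 says: "Patients are already randomised prior to surgery to avoid delays with surgery". Section 5.3 agrees: "Participants will be randomised to either the treatment as usual (TaU) or the intervention group (Viscoseal) any time up until the day of surgery".

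**The concern.** A Cox model needs a response made up of a time and an event indicator. A VDS reading in mm, a girth in cm and a Lysholm or WOMET total are none of these. As the protocol describes its outcomes, the named model has nothing to be fitted to.

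The second problem is the covariates. Length of stay and the type of analgesic given after surgery are settled after allocation. Viscoseal is expected to reduce pain, and pain can influence both what is prescribed and when a patient goes home. Conditioning on a consequence of treatment can remove part of the treatment effect or distort it.

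At stake is the only covariate-adjusted analysis that the protocol names. It covers pain, the domain of the primary outcome, as well as swelling and function. If it were quietly replaced once data were available, the model, any event definition and the covariates would all be open to choice at that stage.

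**Working it through.** No figure in the plan has to be reproduced here. The check sets the sections side by side.

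**1. Is there a time-to-event outcome?** Table 2 (Section 5.5.2) gives these post-operative assessments:

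| Outcome | Form | Post-operative visits in Table 2 | Number |
|---|---|---|---|
| VDS pain at rest | 100 mm scale | 48 h, days 7 and 14, weeks 12 and 26 | 5 |
| VDS pain on walking | 100 mm scale | weeks 12 and 26 | 2 |
| Short-form McGill | score | 48 h, days 7 and 14 | 3 |
| Limb girth | cm | day 14, week 12 | 2 |
| Lysholm, WOMET | scores | weeks 12 and 26 | 2 each |

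Neither Section 8 nor Appendix 1 gives a threshold, event, time origin or censoring rule for any of them. The items that are events by nature (return to theatre or hospital, wound infection, thromboembolism) stand in Section 8.3 under a descriptive safety overview and are not the targets of the Cox model.

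**2. Could an event be built from the scores?** One could define, say, the first visit at which a score crosses a threshold. The crossing would be known only to lie between two visits, and the recorded times would follow the visit schedule. If all 52 patients reached such an event, an outcome with two visits would average 52 / 2 = 26 patients per nominal event time; resting VDS would average 52 / 5 = 10.4. The times would be heavily tied and interval-censored, and the threshold would still have to be invented.

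**3. Could the score stand in for time?** The protocol does not say so. The result would be a hazard ratio, which cannot be read against the 15 mm difference on which the trial is powered (Sections 5.5.1 and 8.2), or in cm or points.

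**4. Which covariates arise after randomisation?** Allocation is made before the operation (Sections 3.2.1 and 5.3). Of the eight listed variables:

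- Sex, age, height, weight and BMI (5) are pre-randomisation characteristics.
- Length of stay and type of post-surgery analgesics (2) are determined afterwards.
- Type of anaesthetic (1) is applied afterwards, but Section 3.2.1 says "All patients receive general anesthesia and a pneumatic tourniquet is used", so it should vary little. The point does not rest on it.

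So 5 + 2 + 1 = 8, with two clear post-randomisation variables. If the phrase pointed instead to the procedure data in Section 8.1, the problem would remain: that list holds operative and post-operative items, again including length of stay and analgesics.

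**5. What is missing from the list?** The baseline value of the outcome is not in it, although Table 2 collects a pre-operative value for every outcome in the table above.

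**6. What does not depend on the Cox model?** The sample size (Section 6.1) and the primary comparison (Section 8.2) use the Mann-Whitney U-test. The secondary outcomes have their own unadjusted tests in Section 8.3.

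**The case against.** The strongest reply is that this is one sentence about a supplementary analysis. The primary test, the power calculation and every unadjusted secondary comparison stand without it. That is right, and it limits the weight of the point.

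A second reply is that event definitions and censoring rules are commonly left to a statistical analysis plan, which is not at hand. That would answer a complaint of missing detail. It does not answer this one: the protocol itself names a method that does not suit the outcomes as it describes them. A later plan could define a threshold event, so it would be too strong to say that a Cox model could never be fitted; it would be a coarse choice with two to five visits.

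Third, the covariate phrase is not itemised. A reader might infer one model with arm and all eight variables, 1 + 8 = 9 terms or more in 52 patients. The protocol does not say that they enter together, so overfitting cannot be charged to it.

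Fourth, the bias may be small. Section 3.2.1 plans day surgery with same-day discharge, so length of stay should vary little. The listed variable is the type of analgesic; analgesic use is a separate repeated measure in Table 2, and it would be wrong to treat the two as one. Both listed variables still arise after allocation, which is enough to make them unsuitable as adjustment covariates.

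Finally, a reader might object to height, weight and BMI together. They are closely related, but this mainly inflates their own standard errors and should leave the treatment coefficient largely unaffected. It is minor.

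**Conclusion.** The sentence is wrong as written. The only covariate-adjusted analysis named in the protocol does not match its outcomes and would not yield an interpretable effect in mm, cm or points. Two of the eight covariates most naturally meant arise after randomisation, and adjusting for them can bias the treatment effect.

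The reach is limited to this supplementary analysis of pain, swelling and function. A reader might conclude that the trial's primary result is compromised; it is not, because the day-7 comparison is a Mann-Whitney U-test. A reader might also assume a large bias from the covariates; the protocol gives no figures from which its size could be judged.

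The covariate part assumes that the phrase refers to the list directly above it in Section 8.3. The model part needs no such assumption.

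**What to change.** Replace the Cox sentence in Section 8.3 with a model for scores at fixed visits:

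- **Model.** ANCOVA at a single visit, or a repeated-measures mixed model across visits with arm, visit and arm-by-visit terms. Section 6.1 treats the VDS as ordinal, so a proportional-odds model is equally defensible there; the choice should be stated in advance for each outcome.
- **Terms.** Arm, the baseline value of the same outcome, the randomisation sequence (the two in Section 6.1.1: 24 patients in the MRI sub-study, 28 in the main trial only), and at most a few named pre-randomisation covariates such as age, sex and BMI.
- **Reporting.** Adjusted effects with 95% confidence intervals.
- **Removed covariates.** Drop length of stay and post-surgery analgesics from the model, summarise them by arm, and stop describing them as baseline characteristics.
- **Girth visits.** Table 2 has day 14 and week 12 after surgery; Section 8.3 has days 7 and 14. The two must be reconciled before the swelling model can be fixed.

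The model change is a wording amendment: no extra patients and no new measurements. Reconciling the girth visits may affect what is collected, depending on which schedule has been followed.
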